5.4 Rationale for the selection of the study population

Sleep disruptions in adults with frequent nocturia complaints are very common. One survey identified that going to the bathroom was the most frequent cause for waking up at night in adults and it increased with age [Ohayon 2008]. The severity of the nocturia defined by the number of awakenings for voiding has been shown to correlate with the severity of sleep disruption as well as with impaired quality of life in patients [Drake 2005]. While nocturia is a multifactorial condition that can have several origins, it is usually split into three categories:

1. Nocturnal polyuria:

These patients have a large production of urine during sleep, usually related to alterations in biological master clock regulations, large liquid intake before bedtime, diurnal perturbations of antidiuretic hormone, and increased atrial natriuretic peptide release with increasing age [Van Kerrebroeck 2002].

2. Bladder storage problems:

These symptoms are of neurogenic or myogenic origins. The storage problems can have several causes, e.g., by detrusor overactivity caused by secondary conditions such as benign prostatic hyperplasia, bladder hypersensitivity, or urogenital aging.

3. Nocturia due to global polyuria:

This population will not be included in this study, as these subjects usually have other severe underlying conditions that would make participation in this trial unfeasible. For example, subjects with severe global polyuria require large fluid intake, including at night, which would directly influence the defined study outcomes. However, subjects on stable treatment for type 2 diabetes mellitus for at least 3 months will be allowed to participate if study criteria are met.

While pharmacological interventions exist to relieve nocturia complaints, the comorbid sleep disruption is usually left untreated even though its treatment has been associated with improvement in the overall clinical outcome for these subjects. This indicates that sleep disruptions may not necessarily be a consequence of nocturia, but also the cause for the nocturnal voidings. There is a high unmet medical need to identify effective and safe treatments that target the frequent sleep complaints in this population.

5.5 Contraception requirements for women of childbearing potential

No contraceptive methods are needed for female subjects participating in this clinical study as women of childbearing potential will not be included.

5.6 Contraception for male subjects with a partner who is of childbearing potential

No contraceptive methods are needed for male subjects participating in this clinical study.

5.7 Dietary aspects and physical activity restrictions

During the study, subjects will be instructed about the following restrictions:

- No alcohol consumption within 3 hours before going to bed.
- Avoiding intake of large quantities of fluid before going to bed that will likely result in the need to void.
- No caffeine consumption after 4 pm (this includes also different types of tea such as black or green tea, coffee, caffeinated gums, caffeine tablets).
- No heavy tobacco use leading to inability to refrain from smoking during the night.
- No driving or engaging in activities that require operating vehicles or dangerous machinery within 7 hours following study treatment intake.
- No travelling across ≥ 3 times zones or planned travel across ≥ 3 times zones at any time during the study.
- No daytime naps during the study.

5.8 Screen failures and re-screening

Screen failures are defined as subjects recruited in the clinical study (i.e., ICF fully signed) who are not subsequently randomized in the study. Minimum information includes demography (i.e., age, sex, race, and ethnicity) screen failure details (e.g., eligibility criteria not met, withdrawal of consent), medical history, any SAEs, as well as concomitant medications related to the treatment or occurrence of the SAEs.

It is not permitted to re-screen subjects in this study, however procedures or assessments conducted as part of the subject's routine clinical management (e.g., laboratory sample) and obtained before signing the ICF may be used for screening or baseline purposes [Section 7.1.1]. This includes repeating assessments in the event of exceptional circumstances (e.g., technical issues).

5.9 Criteria for withdrawal and retention of subjects

A subject has the right to prematurely discontinue study treatment at any time, by withdrawal from study treatment only or by withdrawal from study treatment **and** any

further participation in the study (i.e., premature withdrawal from the study). It is recommended that the investigator / authorized delegate makes a reasonable effort to maintain subjects on treatment, as medically appropriate, and follow the schedule of visits, as data robustness depends on such compliance. Should a subject stop treatment or withdraw from the study, the investigator / authorized delegate should ascertain the reason(s), while fully respecting the subject's rights.

Subjects who prematurely discontinue study treatment / the study for any reason will not be replaced, given the low discontinuation rate observed in the clinical program of daridorexant.

5.9.1 Study treatment interruption and premature discontinuation of study treatment

The decision to prematurely discontinue study treatment may be made by the subject, the investigator / authorized delegate, or the sponsor personnel.

The investigator / authorized delegate has the option of temporarily interrupting or prematurely discontinuing study treatment for a given subject in response to an AE, a diagnostic or therapeutic procedure, a laboratory abnormality, or for administrative reasons. If study treatment is interrupted by the subject for any reason, he/she must inform the investigator / authorized delegate as soon as possible. All study treatment interruptions must be recorded in the eCRF.

The investigator / authorized delegate must permanently discontinue study treatment for a given subject if, on balance, he/she believes that continued administration would be contrary to the best interests of the subject.

Study-specific criteria for temporary interruption and permanent discontinuation of study treatment are described in Sections 5.9.1.1, 5.9.1.2, 5.9.1.3 and 5.9.1.4.

The main reason for permanent discontinuation of study treatment (e.g., due to pre-specified study treatment discontinuation criteria, an AE, lack of efficacy, study termination) must be documented in the eCRF.

A subject who prematurely discontinues study treatment is **NOT** considered withdrawn from the study. The subject will be asked to return for a PEOT visit within 5 days of last intake of study treatment and thereafter to attend the following visits up to the respective EOTP visit as defined in the schedule of activities [Table 1] and in Section 7.2. After the EOTP visit has been completed, the subject will perform the Safety Follow-up Phone call 5 to 10 days later which will be considered an EOS visit. All subjects withdrawn from study treatment will be encouraged to follow planned study procedures (e.g., visits, diary, and questionnaire completion [Table 1]) until planned EOS provided that the subject's

consent for this limited participation in the study has not been withdrawn. This will reduce the amount of missing data which is important from a study integrity perspective.

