Daridorexant (ACT-541468) Insomnia and comorbid nocturia Protocol ID-078A401 Version 3

4 September 2023, page 44/122

Objectives	Endpoints in period I and period II			
	• Changes from baseline to Week 1, Week 2, Week 3, and Week 4 in Patient Global Impression of Change (daytime and nighttime symptoms)			
	 Change from baseline to Week 4 in Patient Global Assessment of Disease Severity (daily life) Change from baseline to Week 4 in Patient Global Impression of Change (daily life) 			
	• Change from baseline to Week 2 and Week 4 in EQ-5D-3L score			
	• Treatment satisfaction at Week 4 assessed via NRS			
	• Treatment period preference at Visit 8 (EOTP II)			
To explore a) the sensitivity of the IDSIQ to detect clinical changes in this study population and b) the use of narratives to report subject's perception of treatment effect	 The change from baseline to Week 1, Week 2, Week 3, and Week 4 in all IDSIQ domains The subjects will be asked to complete a narrative at the end of each treatment period. More details on the analysis will be provided in the SAP. 			
To assess the safety and tolerability of daridorexant	Safety endpoints			
	Safety monitoring will include:			
	• Occurrence of TEAEs up to 5 days after EOTP I and/or EOTP II.			
	• Occurrence of treatment emergent AESIs up to 5 days after EOTP I and/or EOTP II.			
	• Occurrence of treatment-emergent serious adverse events up to 5 days after EOTP I and/or EOTP II.			
	Occurrence of TEAEs leading to premature discontinuation of the study and/or treatment.			
	• Change from baseline to EOTP I and EOTP II in vital signs (systolic blood pressure, diastolic blood pressure, and pulse rate).			
	• Change from baseline to EOTP I and EOTP II in morning sleepiness as determined by the scores on the VAS in the morning.			
	• Occurrence of suicidal ideation, suicidal behavior, and/or self-injurious behavior with / without suicidal intent based on the C-SSRS [©] at Visit 1, Visit 4, Visit 5, Visit 8, and Visit 9.			

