9.2.5.1 Adverse events

9.2.5.1.1 Treatment-emergent AEs and SAEs

TEAEs and SAEs will be tabulated by study treatment, SOC, and preferred terms within each SOC: the number and percentage of subjects who experienced at least 1 (S)AE, at least 1 (S)AE within each SOC, and at least 1 (S)AE within each preferred term will be displayed. (S)AEs will also be summarized by decreasing frequency of preferred term. (S)AEs will also be tabulated by maximum intensity and by relationship to study treatment.

AEs and SAEs are considered treatment-emergent AEs and SAEs if they occur up to 5 days after DB study treatment discontinuation.

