#### 7.2 Adverse events

TEAEs are defined as AEs that started or worsened on or after study treatment start date up to the EOT + 5 days (in each treatment period). AEs that start in TP I and continue into TP II will only be presented as TP I AEs, unless there is a worsening in TP II. AEs that start in the washout period (i.e., on day 6 of the washout period up to 1 day prior to start of TP II) and continue into TP II will not be presented for any of the treatment periods.

AEs will be coded using MedDRA. The MedDRA version used for reporting will be specified in the footnote of the applicable output.

The number (%) of study subjects experiencing a TEAE (including SAEs, AESI, and AEs leading to premature discontinuation and/or temporary interruption of study treatment) will be summarized by SOC and/or PT, and/or maximum intensity.

AESIs, defined as AE PTs denoting 'falls' and 'incontinence episodes' will be summarized separately.

A subject with multiple intensities reported for an AE will be summarized under the maximum intensity recorded for the event.

Apart from the summaries of occurrences, where each event is counted, a subject with multiple occurrences of an AE is counted only once in the AE category (e.g., SOC, PT). If a single AE worsens on the same treatment, this event will be considered as one occurrence.

AEs will be sorted by descending frequency, first based on daridorexant 50 mg, then based on placebo. After this sorting, SOCs are presented in alphabetical order and PTs are sorted alphabetically within each SOC.

The following AE summary tables will be provided:

- Treatment-emergent AEs;
- TEAEs related to study treatment;

Page 35/50

Statistical Analysis Plan for Clinical Study Report Version 2 Doc No D-24.149

- AEs leading to premature discontinuation of study treatment;
- AEs leading to temporary interruption of study treatment;
- Treatment-emergent SAEs (including occurrences);
- Treatment-emergent SAEs related to study treatment (including occurrences);
- TEAEs with fatal outcome;
- TEAEs related to study treatment with fatal outcome;
- Total number of deaths;
- Treatment-emergent AESIs;
- AEs during the washout period.

All AEs will be listed, with AESIs and SAEs being flagged in the AE listing.

Separate listings will be provided for AEs leading to premature discontinuation of study treatment, AEs leading to temporary interruption of study treatment, SAEs, fatal AEs, and AESIs.

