#### 10 GENERAL DEFINITIONS AND DERIVATIONS

### **10.1** Treatment start and end dates

Study treatment start or end date is the earliest or latest date, respectively, of dose intake recorded on the 'Study Treatment Log' page for the corresponding treatment period.

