## 10.2 Study periods

The screening period is defined as the time from the informed consent date until one day before the study treatment start date of TP I, or date of screening failure.

The treatment periods are defined as the time from the day of study treatment start until the day of EOT (Week 4), or, for those who prematurely discontinued study treatment (i.e., those without an EOT date), until the day of study treatment end date.

Provided the subject starts the second treatment, the washout period is defined as the time from one day after the end of TP I until the day before start of TP II.

The safety follow-up period is defined as the time from one day after the end of the last treatment period until end of safety follow-up period / EOS date (for both treatment periods).

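### The cut-off for treatment-emergent adverse events is stated inconsistently for subjects who stop treatment early, so off-drug events can be counted under the stopped treatment or not, depending on which rule is programmed

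*Protocol*

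**What the plan says.** Five places in the two documents bear on when the treatment-emergent window closes.

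- **SAP 7.2** counts an AE as treatment-emergent if it "started or worsened on or after study treatment start date up to the EOT + 5 days (in each treatment period"). EOT is spelled out in the abbreviation list, separately from EOTP, but is never given a date definition.
- **SAP 10.2** ends a treatment period at EOT, which it labels Week 4. It then gives a second branch, "for those who prematurely discontinued study treatment (i.e., those without an EOT date), until the day of study treatment end date". SAP 10.1 fixes that end date: "Study treatment start or end date is the earliest or latest date, respectively, of dose intake recorded" on the treatment log for the period.
- **Protocol 5.9.1** has early stoppers come to a PEOT visit and "thereafter to attend the following visits up to the respective EOTP visit as defined in the schedule of activities".
- **Protocol 3.4, Table 3** lists the safety endpoint as "Occurrence of TEAEs up to 5 days after EOTP I and/or EOTP II". The synopsis uses the same anchor.
- **Protocol 9.2.5.1.1** uses a different one: "AEs and SAEs are considered treatment-emergent AEs and SAEs if they occur up to 5 days after DB study treatment discontinuation".

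SAP 11.1 records no change to the planned analyses. SAP 11.3 discloses that the safety follow-up was set to 5 days, but not the date from which the 5 days are counted.

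**The concern.** For subjects who complete a period, the anchors differ by about a day and the choice hardly matters. For early stoppers who stay in the study they can differ by weeks. The SAP 10.2 description of this group presumes that they have no EOT date, yet protocol 5.9.1 sends them to the Week 4 visit, so a compliant early stopper would have one. Two programmers could each follow the SAP in good faith and produce different AE tables.

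What is at stake is the treatment column in which an event appears. Protocol 4.3 gives a half-life of 8 h, so an event weeks after the last tablet says little about the drug. Falls are an adverse event of special interest, and protocol 2.4.3 notes that fall risk is raised in elderly subjects whatever the treatment, so background events off drug are plausible. Exposure under SAP 5.4.1 stops at the treatment end date, so on the wider reading the AE window and the exposure would no longer match.

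**Working it through.** The documents give no figure to reproduce; the check is day arithmetic within one treatment period.

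**Inputs.** The planned period end is Day 29 (SAP section 2), with a visit window of ± 2 days (protocol Table 1). The window adds 5 days to its anchor under every rule. The last-dose day is varied. The discontinuation date in 9.2.5.1.1 is taken as the day of last intake.

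**Formulas.**
- Rule A (protocol 9.2.5.1.1, or the SAP 10.2 branch for discontinuers): window ends on last-dose day + 5.
- Rule B (Table 3 and the synopsis, or SAP 7.2 with EOT read as the Week 4/EOTP visit): window ends on EOTP day + 5.
- Excess of B over A = EOTP day − last-dose day.

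| Last dose | Rule A ends | Rule B ends (EOTP Day 29) | Excess | Excess, EOTP Days 27–31 |
|---|---|---|---|---|
| Day 1 | Day 6 | Day 34 | 28 days | 26–30 |
| Day 5 | Day 10 | Day 34 | 24 days | 22–26 |
| Day 14 | Day 19 | Day 34 | 15 days | 13–17 |
| Day 21 | Day 26 | Day 34 | 8 days | 6–10 |
| Day 28 (completer, EOTP Day 29) | Day 33 | Day 34 | 1 day | – |

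As a share of the Rule B window, the excess is 24/34 = 71%, 15/34 = 44% and 8/34 = 24% for a last dose on Day 5, 14 and 21.

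**How much of this must be in the database.** Protocol 8.2.1 requires AEs to be recorded up to 5 days after treatment discontinuation, which gives 5 − 5 = 0 days beyond Rule A. Footnote 1 of protocol Table 1 says 5–10 days, which gives at most 10 − 5 = 5 days. Later events are not barred: 8.2.1 and 7.2 have AEs asked about at every visit, and early stoppers keep attending visits.

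**How many subjects.** Protocol 9.2.2.4 and SAP 6.1.4 expect dropouts below 3%. Used as a proxy for early treatment stops, this gives 0.03 × 50 = 1.5, or one or two subjects. If the rate is meant for each period separately, the total is 2 × 1.5 = 3 over both periods. One subject in a column of 50 is 1/50 = 2 percentage points.

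**The case against.** The strongest reply is that SAP 10.2 already contains the right rule. It has a branch for premature discontinuers that ends the period at the last intake, and its evident intent is a last-dose cut. On that reading the excess is 0 and the remark about a missing EOT date is only loose wording. EOT is nowhere equated with the EOTP visit date. SAP 7.2 starts washout AEs on day 6 of the washout period, which is compatible with a cut at last dose + 5. Protocol 4.1.1 even describes EOTP as reached on the morning after the last intake. Few late events need be recorded, the safety tables are descriptive, and all AEs are listed, so onset relative to last dose can be checked.

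Most of this stands, and it limits the point. A reader might infer that off-drug events up to about four weeks late *are* credited to the stopped drug. The documents do not support that: it requires EOT to mean the visit and the discontinuer branch to be set aside, and four weeks is reached only by a stop after the first dose. Nor do they support a claim that the safety comparison is biased in a known direction, or that the SAP simply contradicts the protocol, since the wider reading matches Table 3.

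The reply does not remove the inconsistency. SAP 10.2 labels EOT as Week 4 and sets it against the study treatment end date, so the two are not synonyms there. SAP 7.2 opens the window with the defined start date but closes it with EOT, although a defined end date was available. It does not refer to the 10.2 branch, whose stated condition a compliant early stopper fails. Protocol 5.9.1 uses EOTP as a scheduled visit after PEOT. The two protocol anchors conflict on their face.

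**Conclusion.** The point holds as an inconsistency between stated rules, not as a demonstrated misattribution. For an early stopper who attends EOTP on Day 29, the window closes either at last dose + 5 or on Day 34. The gap is 24, 15 or 8 days for a last dose on Day 5, 14 or 21, and at most 28 (30 if the visit falls on Day 31). Under the SAP 10.2 branch for discontinuers it is 0.

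The practical effect is likely to be small. It rests on the assumption that the dropout figure is a fair proxy for early treatment stops, for which the documents give no rate, and on how many events are entered beyond the mandatory recording limit. Neither allows a direction of bias to be stated. It is still worth settling before the AE tables are programmed, because one event shifts a percentage by 2 points and the remedy is cheap.

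**What to change.** 1. In SAP 7.2 and 10.2, set one cut-off for every subject: onset or worsening up to the study treatment end date of that period, as defined in SAP 10.1, + 5 days. This agrees with protocol 9.2.5.1.1. EOT should be defined, or dropped from the AE rule.
2. Delete the parenthetical in SAP 10.2 that describes early stoppers as lacking an EOT date.
3. Tabulate later AEs separately as off-treatment. Include subjects who never start TP II: SAP 10.2 defines a washout period only for those who start the second treatment, and SAP 7.2 provides no separate table for later follow-up events.
4. Reconcile protocol Table 3 and the synopsis with 9.2.5.1.1. The AE recording limits in 8.2.1 and in footnote 1 of Table 1 also differ and must be reconciled.

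EOTP can stay as the anchor for efficacy. The cost is wording and one date variable, with no new data. The downside is that treatment-emergent counts may fall slightly; the separate off-treatment table keeps those events visible.

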5.9.1.1 Pregnancy / pregnancy plans

If a subject becomes pregnant while on study treatment, study treatment **must** be permanently discontinued. The investigator / authorized delegate must counsel the subject and discuss the risks of continuing with the pregnancy and the possible effects on the fetus. For reporting of pregnancies, refer to Section 8.3.1.

5.9.1.2 C-SSRS[©]

Subjects who answer "yes" to items 1, 2, 3, 4, or 5 on the C-SSRS[©] assessment at any post-randomization visit must undergo further evaluation by the investigator to assess the risk. If a positive answer is provided during the first treatment period, the investigator must interrupt study treatment and confirm the suitability of the subject to remain under treatment. This evaluation and decision must be clearly recorded in the source documents.

5.9.1.3 Concomitant use of forbidden medications

Subjects must not take forbidden medications during the study. However, if the subject is treated with a forbidden medication [Appendix 11], study treatment must be discontinued. See Section 5.9.1 for the handling of subjects that have prematurely discontinued study treatment.

5.9.1.4 Occurrence of complex sleep behaviors while on study treatment

Complex sleep behaviors include sleepwalking, sleep driving, sleep-talking or engaging in other activities while not fully awake (e.g., preparing and eating food, making phone calls, having sex). Subjects who experience a complex sleep behavior event during the study must discontinue study treatment immediately.

5.9.2 Withdrawal from the study

Subjects may voluntarily withdraw from the study without justification for any reason at any time. Subjects are considered withdrawn if they state an intention to withdraw further participation in all components of the study (i.e., withdrawal of consent), die, or are lost to follow-up [see Section 5.9.3]. If a subject withdraws consent for further study participation, no further data will be collected in the eCRF from the date of withdrawal onward. The investigator / authorized delegate may withdraw a subject from the study (without regard to the subject's consent) if, on balance, he/she believes that continued participation in the study would be contrary to the best interests of the subject. Withdrawal from the study may also result from a decision by the sponsor for any reason, including early termination or suspension of the study [see Section 10.10]. Enrolled subjects who prematurely discontinue from the study for any reason will not be replaced.

If, for whatever reason (except death or loss-to-follow-up), a subject is withdrawn from the study, the investigator / authorized delegate should make best efforts to schedule a last appointment / phone call to assess the safety and well-being of the subject, collect unused study treatment and discuss follow-up medical care. Data obtained during this last appointment / phone call will be recorded in the subject's medical records, but it will not be collected in the eCRF.

The main reason for premature withdrawal from the study must be documented in the eCRF.

The investigator must provide follow-up medical care for all subjects who are prematurely withdrawn from the study, or must refer them for appropriate ongoing care, as described in Section 6.3.

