8.2.1 Reporting adverse events

The occurrence of an AE may come to the attention of study personnel during study visits, phone calls, narrative texts or interviews with subjects presenting for medical care.

At each study visit (scheduled or unscheduled), the investigator / authorized delegate will inquire about the occurrence of AEs since the last visit.

All AEs with an onset date after signing the ICF and up to 5 days after study treatment discontinuation must be recorded in the eCRF.

The AE should be reported as a final diagnosis (if possible) rather than a list of symptoms.

Information to be collected on an AE form in the eCRF includes date of onset, action taken with the study treatment, outcome of AE, date of resolution (if applicable), and

investigator / authorized delegate's assessment of intensity as well as relationship to study treatment, study design or protocol-mandated procedures.

Information on worsening of intensity will be collected on a new AE form. If the AE lessens in intensity, no change in the severity is required to be reported.

AEs still ongoing after study treatment discontinuation must be followed up until resolution, until they are no longer considered clinically relevant, or until stabilization.

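### Protocol 5.9.2 keeps last-contact safety data out of the eCRF even when consent still stands, which contradicts the AE recording rule in 8.2.1

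*Protocol*

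**What the plan says.** Protocol 5.9.2 sets up the last contact as follows: "If, for whatever reason (except death or loss-to-follow-up), a subject is withdrawn from the study", the site should try to arrange a final appointment or call "to assess the safety and well-being of the subject, collect unused study treatment and discuss follow-up medical care". What is learned there is kept in the subject's "medical records, but it will not be collected in the eCRF".

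The same section describes three routes out of the study that are neither death nor loss to follow-up:

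- **Withdrawal of consent.** This has its own rule: "If a subject withdraws consent for further study participation, no further data will be collected in the eCRF" from the date of withdrawal.
- **The investigator's decision.** The investigator "may withdraw a subject from the study (without regard to the subject's consent)" when staying in would be against the subject's best interests.
- **The sponsor's decision.** "Withdrawal from the study may also result from a decision by the sponsor for any reason", and this includes early termination or suspension of the study.

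Protocol 8.2.1 states: "All AEs with an onset date after signing the ICF and up to 5 days after study treatment discontinuation must be recorded in the eCRF". It makes no exception for withdrawn subjects. Protocol 8.1.1 defines falls and incontinence episodes as the AEs of special interest (AESIs) and puts fall details on an eCRF form. SAP 7.2 counts an AE as treatment-emergent up to 5 days after end of treatment in each period.

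**The concern.** A contact whose stated purpose includes a safety assessment produces data that the protocol then keeps out of the study database. For a subject who has withdrawn consent that is understandable, and 5.9.2 already provides for it. For a subject removed by the investigator or the sponsor, whose consent may still stand, the documents give no reason for it, and it conflicts with 8.2.1.

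The AE and AESI tables are built from these records, and Table 3 of Protocol 3.4 lists among the safety endpoints "Occurrence of TEAEs leading to premature discontinuation of the study and/or treatment". There is no independent data monitoring committee (Protocol 4.4), and safety oversight is continuous review by the sponsor (Protocol 10.9). Information left in site charts is therefore missing from the analysis and may not reach that review.

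**Working it through.** The plan gives no figure on this point to reproduce. The check is a comparison of texts, followed by a sense of scale.

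**1. Do the two rules meet in the same case?**

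| Question | Protocol 5.9.2, last contact | Protocol 8.2.1, AE recording |
|---|---|---|
| Which subjects? | All withdrawn, except by death or loss to follow-up | All, no exception |
| Which information? | Whatever is obtained at the last contact | Every AE with onset from consent to 5 days after treatment discontinuation |
| Into the eCRF? | No | Yes, mandatory |

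The window in 8.2.1 is tied to onset relative to treatment discontinuation. It depends neither on the date of study withdrawal nor on the date of the report. 8.2.1 also names phone calls as a way in which AEs come to light. So if an AE began inside the window and is first mentioned at the last contact, one section requires it in the eCRF and the other bars it. If the event is a fall, the eCRF fall form in 8.1.1 is caught in the same conflict.

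**2. What is outside the conflict?**

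- SAEs: 8.2.2 sends them to the sponsor on a separate SAE form.
- AEs already known before the last contact: 5.9.2 does not touch them.
- Subjects who stop only study treatment: under 5.9.1 they are not withdrawn, they have a premature end-of-treatment visit within 5 days of last intake, and they are asked to continue visits.

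What remains is non-serious AEs, including non-serious falls and incontinence episodes, with onset in the window and first learned of at the last contact, in subjects withdrawn by the investigator or sponsor.

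**3. Scale.** Inputs are about 50 randomized subjects (Protocol 6.1.4) and expected dropout below 3% (Protocol 9.2.2.4, SAP 6.1.4). Taking 3% as the ceiling and treating dropouts as independent:

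- Expected dropouts, all reasons: 0.03 × 50 = 1.5.
- P(at least 1) = 1 − 0.97^50 = 0.78. The same binomial gives 0.44 for at least 2 and 0.19 for at least 3.
- Weight of one lost event in a treatment column of about 50: 1/50 = 2 percentage points.

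The 1.5 covers every reason for dropping out, including consent withdrawal, loss to follow-up and death, so the affected group is only a part of it. The documents give neither a split by reason nor an AE rate among withdrawn subjects, so the number of lost events cannot be computed.

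**4. A related mismatch.** The first footnote to Table 1 of the protocol requires AEs and SAEs to be reported up to 5–10 days after treatment discontinuation. Protocol 8.2.1 and 8.2.2 say 5 days. The window that decides which last-contact events must be recorded is therefore itself stated in two ways.

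**The case against.** The best defence of the text is that 5.9.2 first describes withdrawn subjects as those who withdraw consent, die or are lost to follow-up. Removing the last two leaves only consent withdrawal, where no further data are collected anyway. This does not hold. The sentences that follow add the investigator and sponsor routes, and the last-contact rule applies to any reason but two. Limited to consent withdrawal, it would also largely repeat the rule already given.

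The objections to the consequences are stronger, and most of them stand. A reader might infer that the plan loses events in the very subjects most likely to have them. The documents do not show that. A subject with a tolerability problem can stop treatment and stay in the study, and a complex sleep behavior leads to treatment discontinuation under 5.9.1.4, not to study withdrawal. The higher risk is plausible for withdrawals in the subject's best interests, but no figure supports it.

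A reader might also infer that the tables on discontinuation are biased downwards, more so for the less well tolerated treatment. That does not follow either. An AE that prompts a withdrawal is normally known before the decision, and so falls under 8.2.1 before any last contact. Section 5.9.2 requires the main reason for withdrawal in the eCRF, and SAP 5.1.3 builds the discontinuation summaries from the study treatment log and end-of-study pages.

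Nor is the last contact the only way to learn of an event. 8.2.1 also recognizes interviews with subjects presenting for medical care, and 5.9.2 requires follow-up care for withdrawn subjects.

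**Conclusion.** The contradiction between 5.9.2 and 8.2.1 is certain on the text, and the exclusion is wrong as written for subjects who have not withdrawn consent. Its severity is minor. It puts at risk only non-serious AEs and AESIs inside the window that first surface at the last contact. On the plan's own dropout expectation, this concerns some fraction of at most about 1.5 expected subjects out of 50, possibly none, at about 2 percentage points of an incidence per lost event.

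That size assumes that dropout stays below 3%. It would not apply if the sponsor terminated or suspended the study early, because subjects still in the study could then come under the exclusion together. Neither the direction nor the size of any bias can be derived from the documents. SAE reporting and the primary endpoint are not affected.

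**What to change.** In Protocol 5.9.2, limit the exclusion from the eCRF to subjects who have withdrawn consent. Add that, for subjects withdrawn by the investigator or the sponsor, AEs and AESIs learned of at the last contact with onset inside the reporting window are entered in the eCRF as 8.2.1 requires, and SAEs are also reported as 8.2.2 requires. In the same edit, reconcile the 5-day window in 8.2.1 and 8.2.2 with the 5–10-day window in the footnote to Table 1.

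The cost is about one sentence in 5.9.2 and an aligned footnote. The contact and the AE form already exist, so the only added work is data entry for a few subjects at most under the planned dropout.
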